## APPROACH

***Our central hypothesis is that the bile acid pathway (fasting serum BA, C4, FGF-19, fecal 48h BA excretion) is altered in obesity resulting in reductions in satiety-related hormones, such as FGF-19, PYY, or GLP-1.*** This central hypothesis will be investigated in one specific aim: To characterize the bile acid pathway, key elements of the enterohepatic bile acid regulation and incretin pathway in obesity compare to health (normal weight) at three different metabolic stages: 1) at baseline, and either 2) stimulated by 100 grams of fat diet (standard, validated diet for testing bile acids) or 3) on a low calorie diet with <3% weight loss.

**Rationale:** Recent advances on the **understanding of bariatric surgery** suggest that bile acids play a role in the surgery-related improvement of diabetes. RYGB is associated with doubling of the concentration of serum bile acids, and an increase in serum adiponectin and GLP-1. In rodents, BA delivered to the ileum induces weight loss and improves glucose homeostasis. These results are mainly mediated by the BA receptor, GPBAR1 (also known as TGR5). GPBAR1 stimulation results in a rapid increase in incretins, reduced appetite and improvement in insulin sensitivity. However, the role of bile acids and the key components of the bile acid pathway and enterohepatic circulation have not been elucidated in individuals with obesity.

**Preliminary data:** We recently identified a GPBAR1 gene variant associated with lower BMI, higher satiation (reduced food intake) and higher GLP-1 concentration; and demonstrated that obesity is associated with decreased fasting fibroblast growth factor 19 (FGF-19), a surrogate of ileal BA reabsorption. Interestingly, in mice, the BA effect on GLP-1 secretion is blunted in the absence of GPBAR1.

**Aim:** 1a) To characterize the bile acid pathway, key elements of the enterohepatic bile acid regulation and incretin pathway in obesity compared to health (normal weight) at three different metabolic stages: 1) at

baseline, 2) stimulated by 100 grams of fat diet (standard, validated diet for testing bile acids) and 3) on a low calorie diet with <3% weight loss.

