**Experimental design:** We screen up to 45 participants and will study a total of 38 participants[ 14 individuals with a normal weight (BMI 18.5-25), 24 individuals with obesity (BMI >30)] to compare bile acid pathway, key elements of the enterohepatic bile acid regulation and incretin pathway in obesity compare to health (normal weight) at three different metabolic stages: 1) at baseline, 2) on a 100 grams of fat diet, or 3) on a low calorie, low fat diet. Participants will be on each diet for one week prior to collection of samples; with one week on regular diet between the high fat/high calorie diet and the low calorie diet. Diet will be provided by the metabolic kitchen. Participants will present after an overnight fast to the CRTU on day 5 and day 7 for testing. On day 5 participants will undergo a flexible sigmoidoscopy procedure from which a biopsy will be obtained. A bowel cleansing with water enema will be given by a CRTU nurse before the procedure. On day 7, participants will consume their "scheduled meal" and blood samples will be collected at -15, 0, 15, 30, 45, 60, 90, 120, 150, 180, 210, 240, 300, 360 minutes. Fasting and postprandial blood samples will be used to analyze, metabolomics, PYY, GLP-1, FGF-19, C4, BA, and short-chain fatty acids (SCFA). Plasma will be collected to analyze EV. Fasting saliva sample will be collected for GI peptide and metabolomics. VAS ratings of appetite and satiation will be recorded during the day every 15 minutes for the first 90 minutes, then every 30 minutes. Prior to discharge from the CRTU, participants will meet with study staff to discuss the following week's diet. On day 5 and 6 (48 hours), stool from every bowel movement will be collected for fecal BA, SCFA and microbiome. Participants will repeat the studies for a total of three times.

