## STATISTICAL ANALYSIS

**Endpoints:** *Primary endpoint:* Fecal BA excretion in obesity vs. health and the change from baseline with high fat/high calorie diet vs. low calorie diet. *Secondary endpoints:* (a) fecal individual BA and SCFA excretion; (b) fasting serum C4 and FGF19; (c) serum BA; and (d) serum fasting, peak and AUC postprandial FGF-19, GLP-1 and PYY.

**Statistical analysis:** The proposed analyses are based on analysis of covariance models, with the responses being each variable compared to baseline. The covariates to be considered include gender and BMI.

**Sample size:** In healthy volunteers, the normal value for fecal BA is  $957 \pm 185$  micromoles/48hours (SEM). The table below summarizes data for primary endpoint considering the mean difference between two groups (healthy vs. obesity) and difference between baseline to high fat vs. low fat diet in each group (healthy vs. obesity), n=8 per group; and estimates the effect size detectable with 80% power based on a two sample t-test at a two-sided  $\alpha$  level of 0.05. We will accrue 38 participants to achieve the above given n value, assuming a 20% dropout rate.

Response	Mean	SD	Predicted differences [% (absolute #)] n=8/group
Fecal BA, $\mu$ moles/48hours	957	185	1) Patient with obesity compared to health: 25% (258 $\mu$ moles/48h) 2) Baseline compared to high fat vs. low fat diet: 24% (233 $\mu$ moles/48h)

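### The accrual of 38 does not follow from 8 per group with 20% dropout in the design as scheduled (20 would suffice), so the printed detectable differences do not describe the planned sample

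*Combined protocol and SAP*

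**What the plan says.** The Sample size paragraph of STATISTICAL ANALYSIS covers two comparisons for fecal bile acid excretion: health against obesity, and "difference between baseline to high fat vs. low fat diet in each group (healthy vs. obesity), n=8 per group". It "estimates the effect size detectable with 80% power based on a two sample t-test" at a two-sided 0.05 level. It then links this to enrolment: "We will accrue 38 participants to achieve the above given n value, assuming a 20% dropout rate". The table beneath prints 258 µmol/48h for obesity against health and 233 µmol/48h for diet, both headed as 8 per group.

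The experimental design under APPROACH divides the 38 into "14 individuals with a normal weight (BMI 18.5-25), 24 individuals with obesity (BMI >30". The ABSTRACT gives the same 14 and 24.

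On who takes which diet, the operational text is consistent:
- The schedule table in APPROACH is a single four-week calendar with a baseline week, a high-fat week, a second baseline week and a low-calorie week.
- METHODS lists one sequence of visits for all participants and has meals supplied in weeks 2 and 4.
- The experimental design says the studies are done three times in each participant.

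Against this, the opening of APPROACH describes the stages as "1) at baseline, and either 2) stimulated by 100 grams of fat diet" or the low-calorie diet, and the experimental design also has 'or' before the third stage. The aim in the ABSTRACT, and the aim restated later in APPROACH, both use 'and'.

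**The concern.** The sentence on accrual is the only reason the document gives for enrolling 38 people. If 38 is not what 8 per group at 20% dropout requires, two things follow.

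First, the detectable differences for the primary endpoint belong to a sample the study does not plan to have, so a reader is misinformed about its sensitivity. Second, each participant is scheduled for three unsedated sigmoidoscopies with biopsies, and a reader would take 38 to be the number needed for 8 per group when the scheduled design needs far fewer. A larger sample may well be justified, but the document does not say why, nor why the ratio is 14:24.

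**Working it through.** **Inputs.** From STATISTICAL ANALYSIS: 8 per group, 20% dropout, 80% power, two-sided 0.05, two-sample t-test, mean 957 and variability 185 µmol/48h. From APPROACH: 14 normal weight and 24 with obesity. The number of groups to which the 8 applies is not stated, so several are tried.

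**Step 1. Reproduce 38.** Accrual = 8 × groups ÷ (1 − 0.20). The common shortcut multiplies by 1.20 instead.

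| Groups | Completers needed | ÷ 0.8 | × 1.2 |
|---|---|---|---|
| 2 | 16 | 20 | 19.2 |
| 3 | 24 | 30 | 28.8 |
| 4 | 32 | 40 | 38.4 |
| 6 | 48 | 60 | 57.6 |

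Only four groups come near 38, most closely with the shortcut. Four groups would be two weight groups, each divided by diet. The shortcut does not fully allow for a 20% loss: 38 × 0.8 = 30.4, below 32.

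**Step 2. Apply the scheduled design.** Every participant takes both diets, so there are two independent groups. The requirement is 8/0.8 = 10 per group, 20 in total; 38/20 = 1.9 times that.

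**Step 3. Test the 14/24 split.**
- Two groups: 14 × 0.8 = 11.2 and 24 × 0.8 = 19.2 completers, not 8 and 8.
- Four cells: each weight group needs 2 × 8 = 16 completers. Fourteen normal-weight participants cannot supply 16 even with no dropout; after 20% loss they give 11.2/2 = 5.6 per cell. The obesity group gives 19.2/2 = 9.6 per cell, which is enough.

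The split therefore fits neither design.

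**Step 4. Between-group detectable difference, taking 185 as an SD.**
- Normal approximation at 8 vs 8: (1.960 + 0.842) × 185 × √(1/8 + 1/8) = 259. This is close to the printed 258.
- t-test (noncentral t) at 8 vs 8: 1.507 × 185 = 279. Power for 258 is 74%.
- t-test at 11 vs 19: 1.100 × 185 = 203. Power for 258 is 94%.

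The gap between 279 and the printed 258 comes from t-test versus normal approximation. The fall from 279 to 203 comes from the larger number of completers.

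**Step 5. Diet difference.** The printed 233 is not reproduced at 8 per group. A two-sample calculation gives 259 (normal) or 279 (t). A paired calculation that treats 185 as the SD of change gives 183 (normal) or 214 (t). In the scheduled design this contrast is within participants and needs an SD of change, or a within-person correlation. The documents give neither, so no replacement figure can be computed from them.

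**The case against.** The strongest reply is that 38 does have a plausible origin: 4 × 8 × 1.2 = 38.4, and the choice between dividing by 0.8 and multiplying by 1.2 moves the total by only about two people. That stands. A reader might infer that 38 cannot be obtained under any reading; for the bare total the documents do not support this. What fails under the four-cell reading is the 14/24 split and a true 20% loss. Nor can one conclude that the study was once a four-cell design: the 'either/or' may be loose wording, and nothing records where 38 came from.

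A second reply is that the harm is small. Both expected groups exceed 8, and on the stated inputs the health-versus-obesity comparison gains power, so the printed 258 is conservative for the planned sample. This also stands. A reader might infer that the study is underpowered, or that enrolling 38 cannot be justified. The documents support neither; they simply do not explain the number.

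A third reply is that 203 and 279 depend on 185 being an SD. The table labels it so, but the sentence beginning "In healthy volunteers, the normal value for fecal BA is" labels it an SEM. This is correct, and if 185 is an SEM neither figure holds. The accrual arithmetic in Steps 1 to 3 does not use 185 and is unaffected.

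**Conclusion.** The stated derivation is wrong as written for the design as scheduled. Eight completers per group at 20% dropout require 20 participants, not 38. The 14/24 split delivers about 11 and 19 completers, and it matches neither the two-group nor the four-cell reading. The differences printed for 8 per group therefore do not describe the planned sample.

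This is a defect of justification and reported sensitivity, not a shortage of participants for the between-group test. The accrual finding rests only on the stated dropout and on every participant taking both diets, which the schedule, visits and diet text all show. The size of the change in detectable difference, from about 279 to about 203 µmol/48h by t-test, rests in addition on 185 being an SD. The correction should be made; it does not call the conduct of the study into question.

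**What to change.** In STATISTICAL ANALYSIS, Sample size:

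1. Replace the accrual sentence with: *We will accrue 38 (14 normal weight, 24 obesity); with 20% dropout about 11 and 19 are expected to complete all three periods.* Add the reason for 38 and for 14:24, since stating expected completers does not by itself justify the number.
2. Settle whether 185 is an SD or an SEM and label it the same way in text and table.
3. Then restate the between-group detectable difference for 11 vs 19 with the t-test the plan names: about 203 µmol/48h at 80% power if 185 is an SD.
4. Restate the diet difference as a within-participant contrast, with the assumed SD of change given and its source named.

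In APPROACH, reconcile the wording of the stages with the schedule: in the opening statement of the aim, drop 'either' and change 'or' to 'and'; in the experimental design, change the single 'or' before the third stage to 'and'.

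The cost is a few sentences, one between-group recalculation once the SD/SEM label is settled, and one new assumption for the diet contrast. No participants or procedures are added.

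### The sample-size table gives the obesity-versus-health difference as both 25% and 258 µmol/48h, but 258 is 27% of the plan's mean of 957, and neither figure has 80% power under the named t-test at 8 per group

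*Combined protocol and SAP*

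**What the plan says.** All the material is in the Combined protocol and SAP, section Statistical Analysis, under Sample size.

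- The text gives a healthy-volunteer mean fecal bile acid excretion of 957 µmol/48h with a spread of 185, which it labels an SEM. The table repeats 957 and 185 under the headings Mean and SD.
- The results column is headed "Predicted differences [% (absolute #)] n=8/group", so each row states one difference in two units.
- Row 1 reads "Patient with obesity compared to health: 25% (258". Row 2 reads "Baseline compared to high fat vs. low fat diet: 24% (233". Both absolute values are in µmol/48h.
- The text says that the table "estimates the effect size detectable with 80% power based on a two sample t-test at a two-sided" level of 0.05.
- On enrolment it says: "We will accrue 38 participants to achieve the above given n value, assuming a 20% dropout rate". The Experimental design paragraphs (Abstract and Approach) split the 38 into 14 participants with normal weight and 24 with obesity.

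**The concern.** The two numbers in row 1 should be the same effect, and they are not. Fecal bile acid excretion in obesity versus health is the first half of the primary endpoint, and this cell is the plan's only statement of the difference that comparison can detect. A percentage is what a reader carries into interpretation, and here it is the more favourable of the two figures. As the cell stands, nobody can tell whether 25% or 258 was the planned target, and the 80% attached to it cannot be true of both.

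**Working it through.** **Inputs** (Statistical Analysis, unless stated): mean 957; SD 185 as headed in the table; 8 per group; two-sample t-test, two-sided 0.05, 80% power; differences 258 (25%) and 233 (24%); planned groups 14 and 24 (Experimental design); dropout 20%.

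**1. Reproduce the plan's absolute figure.** The standard error of the difference is 185 × √(2/8) = 92.5. By normal approximation, the difference detectable with 80% power is 92.5 × (1.960 + 0.842) = 259. Power at 258 is Φ(258/92.5 − 1.960) = Φ(0.829) = 79.7%. So 258 appears to be the calculated value, obtained with a normal approximation.

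**2. Check the percentages against 957.**
- Row 2: 233/957 = 24.3%, shown as 24%. This fits. (Row 2 is used here only to identify the base; how 233 was derived is not examined.)
- Row 1: 258/957 = 27.0%, shown as 25%. This does not fit. 25% of 957 is 239.25.
- For 258 to round to 25%, the base would have to lie between 258/0.255 = 1012 and 258/0.245 = 1053. The plan gives no such mean.
- The average of the two group means as base gives 258/(957 + 129) = 23.8% if obesity is higher, or 258/(957 − 129) = 31.2% if it is lower. The obesity mean as base gives 258/1215 = 21.2% or 258/699 = 36.9%. None gives 25%.

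**3. Power at the stated 8 per group, SD 185, two-sided 0.05.** The t-test column uses the noncentral t distribution with 14 degrees of freedom and noncentrality difference/92.5.

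| Difference (µmol/48h) | % of 957 | Named t-test | Normal approximation |
|---|---|---|---|
| 239.25 | 25.0% | 67.2% | 73.5% |
| 258 | 27.0% | 73.7% | 79.7% |
| 278.7 | 29.1% | 80% | not needed |

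The percentage slip costs 73.7 − 67.2 = 6.5 points by the t-test, or 79.7 − 73.5 = 6.2 by normal approximation. The rest of the gap from 80% to 67.2% (80 − 73.7 = 6.3 points) arises because 258 does not reach 80% under the named test. For 80% power at 239.25, the t-test needs 11 per group; 10 gives 78.1%.

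**4. Planned group sizes, same SD and t-test.** After 20% dropout, 14 × 0.8 = 11.2 and 24 × 0.8 = 19.2, so about 11 and 19 completers.

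| Groups | Power at 239.25 | 80% detectable difference |
|---|---|---|
| 14 vs 24 | 96.3% | 179 (18.7%) |
| 11 vs 19 | 90.9% | 203 (21.3%) |

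**5. Dependence on the SD.** Step 2 does not use 185, but steps 3 and 4 do. If 185 is an SEM, the SD is 185 × √(source n). The documents do not give that n. Assuming 8 to 30, the SD is about 523 to 1013, and t-test power at 258 with 8 per group is about 15% down to 8%.

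**The case against.** The strongest reply is that this is one label in one cell and that the trial does not depend on it. The 25% appears nowhere else, and no endpoint, analysis or enrolment number changes when it is corrected. Much of that stands.

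Three stronger readings are tempting, and the documents do not support them.

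- **That the trial is underpowered for a 25% difference.** The shortfall belongs to the 8 per group on which the power statement is made. The plan enrols 14 and 24, and if SD 185 holds, those numbers detect 239 with well over 80% power even after the assumed dropout.
- **That the percentage slip explains the whole fall from 80% to 67%.** It explains about half. The other half is the difference between a normal approximation and the t-test the plan names. For the same reason, changing the label to 27% alone would leave an untrue 80% in place.
- **That a null result would be taken to exclude 25%.** What a null result excludes depends on its confidence interval, whatever the planning table says.

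It is also fair to say that the SEM/SD conflict over 185 is the larger problem. It does not remove this one: the percentage mismatch remains for as long as 258 and 957 stand.

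**Conclusion.** The point holds as an error in a stated figure. Row 1 gives two different effects, 25% (239 µmol/48h) and 258 µmol/48h (27.0%). They are 19 µmol/48h, or 2 percentage points, apart. The printed percentage understates the detectable difference and so flatters the design's sensitivity. On the plan's stated basis neither figure has 80% power by the named test.

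The mismatch rests only on dividing printed figures, with 957 as the base; row 2 supports that base and no other documented mean is available. Every power figure also assumes that 185 is an SD. The correction is worth making because the cell carries the stated sensitivity of half the primary endpoint.

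**What to change.** First settle whether 185 is an SD or an SEM. If it is an SEM, both rows need recalculating from the true SD.

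If it is an SD, restate row 1 so that percentage, absolute value and power agree under the two-sample t-test. Any one of these is consistent:

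- at 8 per group: 29% (279) with 80% power;
- at 8 per group: 27% (258) with its actual 74% power;
- at 8 per group: 25% (239) with its actual 67% power;
- at the planned sizes, with 80% power: about 19% (179) at 14 versus 24, or about 21% (203) at 11 versus 19 completers.

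The last is the most useful, because it describes the trial that will be run. State the percentage base (healthy mean 957) in the column heading. The cost is a short recalculation and an edit to one table cell with its supporting sentence. If 185 is confirmed as an SD, design, enrolment and conduct need not change. At 8 per group the stated sensitivity becomes less favourable; at the planned sizes it becomes more favourable.

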## SIGNIFICANCE

The proposed study will provide an understanding of the role of BA and the BA pathway in obesity vs. health influenced by different metabolic states, or weight loss interventions. The expected adaptations seen in the BA pathway and incretin response may suggest novel mechanism to enhance and maintain weight loss in obesity. Additionally, the strength of our results will be based on studying the “whole” BA pathway *in-unison* and the data gathered will support the next aims and future studies in BA and obesity.

## Potential Pitfalls, precautions taken and ancillary studies

**Feasibility:** The study team, including the co-PI, has a significant experience in clinical research and has validated the described techniques. Furthermore, the team frequently recruits and retains participants for similar studies. **Precautions:** Studies will be performed under IRB guidance. **Ancillary studies:** DNA will be stored for future gene variation studies and fecal samples will be stored for future microbiome studies.
